Executive Functioning (intermediary target) will be assessed using multiple measures. The Delis-Kaplan Executive Function System (D-KEFS)⁶⁵ was specifically designed to detect deficits in high-level cognitive functions, such as from mild brain damage to the frontal lobe⁸⁴ and has demonstrated strong reliability and validity in various clinical populations. We will administer five tests from the D-KEFS that examine components of executive functioning, such as inhibition (the Color-Word Interference Test), cognitive flexibility or switching (Verbal Fluency, Trails Tests, Design Fluency) and Planning (Towers). The Penn Conditional Exclusion Test (PCET)⁸⁵ will be used as a measure of executive functioning in which Veteran participants must perform a computerized sorting task with three shifting sorting principles. The PCET is similar to the Wisconsin Card Sorting Test⁸⁶, a classic test of executive functioning, but it has four alternate test versions that can be administered with comparable validity and reliability, better allowing for repeated testing over time.

Table 2. Assessments and Timeline									
Measure	Baseline	Session 7	Session 13	Session 21	Post Assessment (After Session 26)	3-Month Follow- up	6- Month Follow- up		
Diagnostic Assessment									
Structured Interview for Hoarding Disorder (SIHD)	х								
Mini-International Neuropsychiatric Exam (MINI)	х								
Hoarding severity (Primary Outcome)									
Savings Inventory-Revised (SI-R)	х	х	х	х	Х	х	х		
Functional Capacity (Secondary Outcome)									
UCSD Performance-Based Skills Assessment (UPSA)	x	х	х	х	x	х	х		
UCSD SORT Test (U-SORT)	х	х	х	х	Х	х	х		
Self-Reported Functioning (Secondary Outcome)									
Specific Levels of Functioning test (SLOF)	х	х	х	х	Х	х	х		
World Health Organization Disability Assessment Schedule (WHODAS 2.0)	x	х	х	х	х	х	х		
Quality of Life (secondary outcome)									
Quality of Life in Neurological Disorders (Neuro-QoL)	х	х	х	х	Х	х	х		
Executive Functioning (Intermediary Target)									
Delis-Kaplan Executive Function System (D-KEFS) Color-Word Interference, Verbal Fluency, Trails Tests, Design Fluency, Towers	x	x			x	x	x		
Penn Conditional Exclusion Test (PCET)	х	х			х	х	х		
Avoidance (Intermediary Target)	·				•				
Behavioral Avoidance Test (BAT)	х	х	х	х	х	х	х		
Acceptance and Action Questionnaire 2 (AAQ-2)	Х	Х	Х	Х	х	х	х		

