Adherence to treatment (mediator) will be measured in the following ways: (1) Number of sessions attended; (2) Therapist ratings of homework compliance (0-100%) based on written assignment review and patient report after each session. Composite adherence score will be calculated on a 10-point Likert scale ranging from 0 (Almost never/never adherent) to 10 (Always adherent).

Timeline

The first 3 months of the project are designed to hire staff, train clinicians, the blind raters, and VRAs (Table 3). There will be a total of 7 overlapping study waves, each lasting 12 months, in which we will enroll 9-10 patients. During the last 3 months of the project, we will finalize data analysis, publish the results and determine the next step for competitive funding.

Statistical Plan

Missing data will be minimized by intensive training of the raters in techniques of clarifying answers and checking questionnaires while Veteran participants are on-site. When missing values are identified, several approaches to acquire the necessary data will be employed: (1) if at all possible, Veteran participants will be rescheduled within 24 hours of completion of tests or interviews; (2) if a participant cannot be rescheduled, an effort will be made to send a tester to the individual's place of residence within the same period; (3) missing data will be examined to assess randomness. Missing data (i.e. loss to follow-up) will be tested to determine if it is informative, and the methods developed by Diggle⁸⁷ and Ridout⁸⁸ to test for completely random dropouts will be used to impute missing values. However, the primary data analysis method allows inclusion of subjects with missing data or those who terminated the study early, without relying on data imputation procedures. Furthermore, we will test whether the drop-outs are random or systematic by comparing the drop-outs with the study completers on the baseline data. The importance of missing data will be examined in the second stage of data analysis (see below).

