At the final stage, hypotheses will be tested using Mixed Effects models, a generalized linear model described by Gibbons et al.⁹¹, Hedeker et al.⁹² and Laird et al.⁹³. Responses at baseline, throughout treatment (sessions 7, 13, 21), post treatment (session 26), 3- and 6-month follow-up will be nested within subjects. Intercept and slope will be modeled as random effects nested within subject; Treatment group, time, and group-by-time interaction will be a fixed effect. A fully saturated treatment by time model will be utilized for inference. Co-variance structure will be chosen based on Akaike's Information Criterion (AIC). Data will be analyzed from all randomized subjects on whom we have a baseline assessment and at least one post-baseline evaluation. If it is needed based on analyses on stage one, baseline covariates (e.g., demographics) will also be added to the model. All hypothesis tests will be intent-to-treat, and will be two-sided at the .05 level. We will adjust p-values for multiple testing within each hypothesis separately by using a Bonferroni correction whenever more than one variable is being tested. Although we didn't have any drop-out in out pilot study, we included a drop-out rate of 10% after the baseline assessment but prior to the first post-baseline evaluation in our power analyses.

Hypothesis 1.1-1.3: Relative to those assigned to ET alone, CREST participants will show significant reduction in **hoarding severity** (primary outcome), improvement in **functioning** (both functional capacity and self-reported functioning; secondary outcomes) and improvement in **quality of life** over time.

- Independent Variables: Treatment Groups (CREST and ET), Time points (baseline, throughout treatment (sessions 7, 13, 21), post-treatment (session 26), 3 and 6-month follow-up).
- Dependent Variable: Hoarding severity (SI-R), Functioning (UPSA, USORT, SLOF, WHODAS 2.0.), Quality of Life (Neuro-QOL).

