- Statistical Analysis: The dependent variable will be analyzed by mixed effects model methods as described above. Baseline demographic and other clinically important characteristics at baseline will be assessed for imbalance between the two groups and their association with the outcome using a univariate analysis. Those found to be significantly unbalanced between intervention groups (p < 0.10) and moderately associated with the outcome (p < 0.15) will be included as covariates in the model. We will adjust p-values for multiple testing within each hypothesis separately by using a Bonferroni correction whenever more than one variable is being tested

Hypotheses 2.1: Treatment adherence, improvement in executive functioning, and reduction in avoidance will mediate hoarding symptom reduction in CREST.

Dependent Variables: Hoarding severity (SI-R)

Independent Variables: Executive Functioning (D-KEFS scaled scores and PCET), Avoidance (AAQ and BAT) and Treatment Adherence score.

Statistical Analysis: The effect of mediator variables will be tested following the procedures recommended by Kraemer⁹⁴, Bauman⁹⁵, Cohen and Cohen⁹⁶, and Busemeyer and Jones⁹⁷. Briefly, treatment mediators explain how or why one variable affects the treatment effect and are defined as mechanisms through which a treatment might achieve its effects. The mediator's effect is measured during the treatment and is correlated with treatment choice and may possibly be a result of treatment and have either a main or interactive effect on the outcome. The dependent or outcome measure (SI-R) will be evaluated throughout the study and will be used as a repeated measure for all the available time points. In essence, the slope of each outcome measure on time will be used as a dependent measure. The mediator and bootstrap technique will be used to calculate a 95% confidence interval for mediation effect. Random effects models will be used for analysis and the change score of mediators will be included in the model.

Hypotheses 2.2: Symptom severity reduction and improved functional capacity will mediate improved quality of life in CREST.

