Power analyses are performed for all hypotheses, incorporating the longitudinal nature of the design. Within this design, repeated observations within subjects are potentially correlated. This has a profound impact on the resulting tests of significance⁹⁸. When the within subject correlation is properly incorporated, the repeated measures analysis takes full advantage of all information obtained from each subject, thereby greatly increasing statistical power over methods that compare treatments cross sectionally⁹⁹. Using the method described by Diggle, Liang, & Zeger¹⁰⁰ and Ahn et al.¹⁰¹, power calculations can be made for repeated measures designs under specified assumptions. Hedeker, Gibbons, & Waternaux¹⁰² extend Diggle et al.¹⁻³'s method for various covariance structures. Procedures describes by Hedeker et al.¹⁰² for Random Regression Models which incorporated these principles was used for the proposed study to estimated needed sample size (RMASS program provided by Hedeker for the Random Regression Model). The design assumptions consist of a 2 treatment groups and up to 7 visits (baseline, sessions 7, 13, 21, 26, and 3- and 6-month follow-up) where the slope is the dependent measure. Other assumptions used were alpha-level, nature of the hypothesis (two-sided versus one-sided), drop-out rate, and variance-covariance matrix of the longitudinal data. We assume a Type-I error level (alpha-level) of .01 to 0.05, drop-out rate of 15% and an autoregressive covariance structure. Data reported in the preliminary studies section which included our own pilot studies were used to calculate effect sizes. From the preliminary analysis of pilot study, the estimated standard deviation (SD) for SI-R score ranges from 12.75-12.82 and the between visit correlation coefficient of 0.71. We considered a range of estimates of stand deviations of 12.5, 12.8 and 13.0, and correlations of .45 to 0.70 in our power analysis. We have reported large effect sizes of 1.02 and 1.51 from our previous studies which converted to differences of 60 to 37 for our primary outcome. However, for these calculations, we conservatively selected smallest clinically meaningful differences that we would like to be able to detect. This was then converted to a medium effect size, defined mathematically as a between-group difference increasing linearly from 0 at baseline to .5 SD units at the last time point. Calculations using the above assumptions indicated that the study will have minimum power of 80% to yield a statistically significant result for a medium effect size with the proposed sample size of 136 patients (68 for each of the two groups).

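### The Bonferroni rule is written for p-values and is not carried over to the mediation intervals, which are set at 95% although Hypotheses 2.1 and 2.2 each involve several mediators

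*Combined protocol and SAP*

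**What the plan says.** All references are to the combined protocol and SAP.

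- **Error control.** The final-stage paragraph of the Statistical Plan, placed before the individual hypotheses, states: "All hypothesis tests will be intent-to-treat, and will be two-sided at the .05 level". It also says the team will "adjust p-values for multiple testing within each hypothesis separately by using a Bonferroni correction whenever more than one variable is being tested". The Bonferroni sentence is repeated under Hypotheses 1.1-1.3 but not under 2.1 or 2.2.
- **Mediation analysis.** Under Hypotheses 2.1 the plan cites several published mediation procedures and random effects models containing mediator change scores. The one inferential output it names is: "The mediator and bootstrap technique will be used to calculate a 95% confidence interval for mediation effect". Hypotheses 2.2 is to be handled in the same way.
- **Mediators in 2.1.** They are listed as "Executive Functioning (D-KEFS scaled scores and PCET), Avoidance (AAQ and BAT) and Treatment Adherence score". The Measures section says of the first item: "We will administer five tests from the D-KEFS that examine components of executive functioning". Composites are defined for the BAT and for adherence ("Composite adherence score will be calculated on a 10-point Likert scale"), but none for D-KEFS.
- **Mediators in 2.2.** The hypothesis names symptom severity and functional capacity. The variable list gives SI-R, UPSA, U-SORT, SLOF and WHODAS 2.0.
- **Power.** The Power Analysis opens with "Power analyses are performed for all hypotheses". It then describes one design: two groups, up to seven visits, slope as the dependent measure, and a group difference growing to .5 SD. Alpha runs from .01 to .05, and 136 patients give at least 80% power.

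**The concern.** A rule for adjusting p-values does not by itself alter the coverage of an interval whose level is stated as 95%. An analyst who follows the Hypotheses 2.1 text would produce 95% intervals. If mediators are then called significant one at a time because zero is excluded, the per-hypothesis 5% level is not secured.

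The mediation result is the trial's account of why CREST works. Hypothesis 2 is a numbered hypothesis, set apart from Aims 3 and 4, which the plan labels exploratory. A false positive here would credit the wrong mechanism. The primary SI-R comparison, the sample size and the participants are not affected.

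**Working it through.** **1. Count the mediators.** In H2.1, one score per D-KEFS test gives 5 + PCET 1 + AAQ 1 + BAT 1 + adherence 1 = 9. A single D-KEFS score gives 1 + 1 + 1 + 1 + 1 = 5. In H2.2, SI-R plus the two functional-capacity measures (UPSA, U-SORT) gives 3; adding SLOF and WHODAS gives 5. The Bonferroni rule is triggered on each count if the mediators are tested separately.

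**2. Coverage that matches the plan's own rule.** The stated level is .05 per hypothesis, so each interval needs coverage 1 - .05/k.
- k = 9: .05/9 = .0056, so 99.44%
- k = 5: .05/5 = .01, so 99%
- k = 3: .05/3 = .0167, so 98.3%

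For independent tests the familywise error is then 1 - (1 - .05/k)^k = .0489 (nine), .0490 (five) and .0492 (three). This reproduces the promised .05.

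**3. Benchmark if each 95% interval erred exactly 5% of the time.** The formula is 1 - .95^k: .370 for nine, .226 for five, .143 for three. With equally correlated test statistics, nine give .326 (correlation .3) and .269 (.5); five give .210 and .183.

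**4. Why the benchmark is not the answer.** An indirect effect is the product of two paths, arm to mediator (a) and mediator to outcome (b). It is null if either is zero. When both are zero, the product interval errs far less than 5% of the time. Its error approaches 5% only when one path is real and strong, so the familywise rate was simulated under stated conditions.

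Assumptions, none of them in the documents: one-mediator models, a 95% product-of-paths interval read separately for each mediator, and mediator correlation 0 to .5. N = 116 comes from 136 x .85 = 115.6, using the 15% drop-out in the Power Analysis.

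| True state, all mediators alike | Nine mediators | Five mediators |
|---|---|---|
| Both paths null | about 2% | about 1% |
| 0.3 SD arm shift, b = 0 | about 12-15% | not tabulated |
| One strong path (0.5-0.8 SD arm shift with b = 0, or mediator-outcome r of .3-.4 with a = 0) | about 22-37% | about 15-23% |

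These figures are good to a few points. Other runs of the same kind put the nine-mediator null case at 1-4% and the 0.3 SD case at 9-11%. A small percentile-bootstrap simulation used N = 122 (136 x .90 = 122.4, the 10% drop-out in the Statistical Plan), 300 trials and a Monte Carlo standard error of up to about 3 points. For nine mediators it gave 2-4% with both paths null, 23-48% with only the arm path real, and 6-35% with only the mediator-outcome path real. For five it gave 0.3-1.3% with both paths null (the basis of the 1% above) and 5-26% with one path real.

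**5. Power statement.** The lowest alpha considered is .01, which equals .05/5. The nine-mediator level of .0056 lies below it. No arm-to-mediator or mediator-to-outcome path size appears among the design assumptions, so the 80% describes the two-arm slope difference and cannot be read across to Hypothesis 2.

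**The case against.** A reader might infer that the plan contradicts itself by prescribing unadjusted intervals. The text does not go that far. The Bonferroni rule precedes all the hypotheses and by its wording covers 2.1 and 2.2. Nothing under 2.1 says the intervals are unadjusted, that there is one per mediator, or that excluding zero is the sole criterion. The sentence speaks of a mediation effect in the singular, and the next places several mediators in the model. The random effects models would yield p-values to which the rule could apply, leaving the 95% interval as plain estimation. All of this stands. The fault is therefore an omission: the plan does not say how its rule reaches the interval, and that interval is the only inferential result it names.

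A reader might also infer at least nine mediators. Nine depends on how D-KEFS enters, which is left open; five is equally compatible with the text.

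The most tempting inference is a flat false-mediator rate of 23-37%. The documents do not support it. With truly inert mediators, the simulated familywise error stays below 5% even at 95% coverage. The high range needs one strong path for every mediator and the other path absent throughout. CREST adds cognitive training that the control lacks, so an arm effect on executive scores is intended, and the protocol says hoarding symptoms are correlated with executive dysfunction. A one-path situation is therefore plausible for some mediators. A uniform shift on all nine is a strong assumption, not least because two of them measure avoidance and the control arm receives more exposure sessions (26 against 19).

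**Conclusion.** The point holds as a gap between the plan's error-control promise and its mediation output. If several 95% intervals are read one by one, the 5% level per hypothesis is not guaranteed. The excess ranges from none when both paths are null to roughly four to seven times the nominal level in the strong one-path case with nine mediators (22/5 = 4.4; 37/5 = 7.4). With five mediators the same case gives three to nearly five times (15/5 = 3; 23/5 = 4.6). These multiples rest on the assumed N, correlations and path sizes, and on intervals being read separately.

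The power point holds in a limited form: the Power Analysis claims to cover all hypotheses but describes only a slope comparison between arms. It does not follow that Hypothesis 2 has any particular power, because the documents give no path sizes. The point is worth correcting before analysis, but it does not bear on the primary outcome.

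**What to change.** - **Hypotheses 2.1 and 2.2:** list the mediator scores, including how the D-KEFS tests enter. Replace the fixed 95% with 1 - 0.05/k, where k is the number of mediators in that hypothesis.
- **Alternative for 2.1:** pre-state one score each for executive functioning, avoidance and adherence, so that k = 3, and use 98.3% intervals.
- **Power Analysis:** say that the 80% refers to the two-arm slope comparison and not to the mediation hypotheses.

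The edit is a few sentences. The price is wider mediation intervals, lower power per mediator and a less favourable power statement. As an illustration only, assume a 0.5 SD arm effect on the mediator, a partial mediator-outcome correlation of .30, 58 patients per arm and path powers that multiply. Joint power per mediator is then .761 x .906 = .69 at 95% coverage and .450 x .692 = .31 at 99.44%. The path sizes are not in the documents. The drop shows why a shorter, pre-stated mediator list may be the better choice.

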have an enriched ED sample, we will include individuals between the ages of 45-85. This older sample will allow for increase efficiency in finding Veteran participants with a level of ED, given that we know older adults with HD show ED^{22,31}, and that HD symptoms (which are correlated with ED) may become worse with age⁴⁵. Given the mixed findings on ED in younger HD populations, this will prevent us from having a floor effect, thus ensuring that we have a sample where we can engage targets. Further, with this age range we will be able to examine how aging contributes to treatment outcomes, a gap in the existing research.

Further, in order to ensure that we

Other **inclusion criteria** include (1) Veterans age 45-85; (2) Hoarding Disorder diagnosis outlined by the Diagnostic and Statistical Manual of Mental Disorders, Fifth Edition (DSM-5)⁶ as measured by the Structured Interview for Hoarding Disorder (SIHD)⁶⁷; (3) HD as a primary diagnosis; (4) executive dysfunction as defined by an

impaired scaled score (i.e., <7) on any of the following tests; DKEFS Color-Word Interference, Verbal Fluency, Trail Making, Design Fluency, Tower Test (5) stable on medications for at least 12 weeks, with no pharmacologic changes expected or made during the 12-month study (6) voluntary consent to participate. **Exclusion criteria** includes (1) diagnosis of a psychotic disorder, bipolar I, bipolar II disorder, substance abuse disorder as measured by the Mini-International Neuropsychiatric Interview (M.I.N.I.)⁶⁸ (3) current or history of any neurodegenerative disease; (4) active suicidal ideation; (5) concurrent participation in any form of psychotherapy, or prior ET, CBT for HD, or CREST for HD.

Recruitment and Randomization

Recruitment will take place in through the San Diego VA utilizing existing recruitment method for our HD studies including review of consults submitted to the VA San Diego Anxiety Disorders clinic, posted flyers in the hospital, VA clinician outreach, participation in the San Diego Hoarding Task Force (PI is a founding

member), and electronic media advertisements. The PI on the proposed project is the Program Director of the VA San Diego Anxiety Disorders Clinic, where Veterans with known HD symptoms are referred.

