Our group has a successful history of recruiting HD patients. Since 2009, we have received over 270 geriatric (over age 60) HD referrals and since 2011 we have received over 125 midlife (under age 60) HD referrals. We have received an increase in calls (7 calls per week) since July 2013 due to our established reputation within the VA Healthcare System and San Diego County. Interestingly, through task force participation and electronic advertisements, we have been able to reach Veterans who were previously not receiving services at the VA and were able to enroll them in our local VA healthcare system. Our funded HD studies within the lab have been completed ahead of schedule due to availability of participants. Thus, we will be able to meet our enrollment goals with our existing recruitment system.

Recruitment targets will be 11-12 patients per study wave (see timeline below) for a total of 136 patients, half of whom will be randomly assigned to CREST. Participants will be administered the Hoarding Rating Scale (HRS)⁶⁹ over the phone by the study coordinator. If they score above a 4 on any item on the HRS, they will be scheduled for an in-person baseline assessment in their home to establish eligibility.

Following informed consent, an independent rater will complete a baseline assessment to determine eligibility. After review of the baseline scores, Drs. [name] and [name] (Co-I) will determine eligibility based on consensus. [name], the study statistician, will prepare the randomization table prior to recruitment of subjects. Subjects will be randomized 1:1 ratio to one of two conditions.

Retention

Our group currently has a markedly low attrition rate for HD studies. We have had 0% attrition across 2 open trials^{15,33} and 8 in our current randomized controlled trial (3 for CREST; 5 for control). Participants will be compensated for their baseline, post-treatment and follow-up assessment points (\$80 total; \$20 per assessment) and a bonus of \$20 for completing all assessments as an additional incentive to participate in treatment. We will optimize follow-up with regular patient contact in treatment, mailings to confirm whereabouts (e.g., birthday and holiday cards), and consent to contact at least one person likely to know subject whereabouts.

Treatment Conditions

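### Hypothesis 2.1 should estimate the executive-functioning step as a baseline-adjusted CREST-minus-ET difference in D-KEFS, not as raw change (minor)

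*Combined protocol and SAP*

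**What the plan says.** Inclusion criterion 4 (Patient Inclusion/Exclusion) requires an "impaired scaled score (i.e., <7) on any of the following tests; DKEFS Color-Word Interference, Verbal Fluency, Trail Making, Design Fluency, Tower Test". Under Recruitment and Randomization, "an independent rater will complete a baseline assessment to determine eligibility", and "After review of the baseline scores" two investigators decide eligibility by consensus. Allocation is 1:1 and applies to the patients so admitted.

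Table 2 has the row "Delis-Kaplan Executive Function System (D-KEFS) Color-Word Interference, Verbal Fluency, Trails Tests, Design Fluency, Towers", marked at baseline, session 7, post-treatment, and 3 and 6 months. There is no separate screening administration and no repeat baseline.

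Hypothesis 2.1 in the Statistical Plan states that "improvement in executive functioning, and reduction in avoidance will mediate hoarding symptom reduction in CREST". It lists as predictors "Executive Functioning (D-KEFS scaled scores and PCET), Avoidance (AAQ and BAT) and Treatment Adherence score", and adds: "Random effects models will be used for analysis and the change score of mediators will be included in the model". It does not name the visits that define the change score, does not say which D-KEFS score or composite is used, and does not adjust the mediator for its baseline. The same paragraph describes a mediator as something associated with the assigned treatment, and plans a bootstrap 95% confidence interval for the mediation effect.

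**The concern.** Patients enter because at least one of five scores was low on one occasion. If the change score starts from that occasion, the low scores will on average be higher at retest with no true change. That baseline is the starting point is an inference: Table 2 offers no other pre-treatment D-KEFS, but the sentence on change scores does not say so.

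Executive functioning is the mechanism that separates CREST from ET, and the hypothesis speaks of improvement in CREST. A reader who looks only at the CREST arm, above all at the tests on which patients were impaired, could credit cognitive training with a gain that the entry rule produces. Separately, a raw change score is a less precise basis for the arm comparison than a follow-up score adjusted for baseline.

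**Working it through.** The plan gives no figure on this point, so there is nothing to reproduce.

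**Inputs from the documents.** Entry cut below 7 on any of five tests; 73% of an earlier sample impaired on one or more of four tests (Patient Inclusion/Exclusion); 68 patients per arm (Power Analysis); randomisation after eligibility.

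**Assumptions not in the documents.** Normal scores with SD 3; retest reliability R of .6 to .8; between-test correlation .3 to .5; cut placed at 6.5; no true change. The population mean μ is set so that 73% fail at least one of four tests.

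**1. Tests the patient failed.** Failing any one test guarantees entry, so the expected change on a failed test is SD × (1 − R) × φ(z)/Φ(z), with z = (6.5 − μ)/SD. As a hand check, take correlation .2 (just outside the main range), where the calibration gives μ = 7.8:
- z = (6.5 − 7.8)/3 = −0.433; φ = 0.363, Φ = 0.332, ratio 1.09.
- R = .6: 3 × 0.4 × 1.09 = 1.31 points (simulated 1.32).
- R = .8: 3 × 0.2 × 1.09 = 0.65 points (simulated 0.66).

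Over correlation .3-.5 and R .6-.8, simulation gives +0.56 to +1.25 points.

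**2. A fixed test over the whole sample.** Passed tests fall on retest and offset most of this. In the same setting with R = .6, 79% of candidates qualify, so the share of admitted patients who failed a given test is 0.332/0.79 = 0.42. Passed tests change by −0.74. Net: 0.42 × 1.32 − 0.58 × 0.74 = 0.554 − 0.429 = about 0.12 points (simulated 0.12).

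Over the main range, passed tests fall by 0.42 to 1.10 points. Any fixed test, or the five-test mean, rises by about 0.06 to 0.12 points (0.02 to 0.04 SD).

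Sensitivity:
- With one test a full SD harder than the rest, the largest fixed-test rise was 0.31 points (0.10 SD).
- The 73% comes from patients over 60, while the trial admits from 45. With a population mean of 10, where about 40% qualify, the rise is 0.08-0.37 points per test and 0.5-2.5 on failed tests, for R from .9 to .5.

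**3. The arm contrast and the mediated effect.** In 2,000 simulated trials per setting of 68 per arm with no true change (R = .5, .7, .9; correlation .3; five-test mean):
- Mean CREST-ET difference in change: −0.005 to +0.007 points; rejection 4.5-5.3% at nominal 5%.
- Mediator-to-outcome coefficient on raw change: rejection 4.5-5.8%.
- Mean indirect effect: 0.
- A within-CREST test of mean change: falsely significant in 7-17%.

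**4. Gain from baseline adjustment.** Without selection, Var(change) = 2(1 − R) and Cov(change, baseline) = −(1 − R) in SD units, so their correlation is −√((1 − R)/2). That is −.45 at R = .6 and −.32 at R = .8; the squares, 20% and 10%, are the share of variance removed. With the entry rule the per-test correlation is about −.33 to −.49, a cut of 11-24%. For the five-test mean the cut is 2-7%. Selection therefore accounts for only about 1 to 4 percentage points of the per-test gain.

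**5. Limit of the adjustment.** Where true executive functioning itself predicts the outcome, adding baseline D-KEFS to the mediator-to-outcome model raised rejection of that coefficient to 9-19%, although the mean indirect effect stayed at 0.

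**The case against.** The strongest reply is that no planned test is biased. The plan's product is a confidence interval for a mediation effect. It defines a mediator by its association with treatment, which is a between-arm quantity, and it nowhere plans a test of mean D-KEFS change within CREST. A mean rise common to all patients also leaves the slope of SI-R on the change score unaltered. This stands, and step 3 bears it out.

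A reader might infer from the entry rule that regression to the mean will create a false executive-functioning mechanism. The documents do not support that, because selection precedes randomisation and both arms carry the same shift. Nor do they support taking the 0.6-1.3 points as the size of the problem: the plan names D-KEFS scaled scores and never picks out each patient's failed tests.

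A reader might also infer that the PCET, which plays no part in eligibility, should become the lead mediator. That does not follow. It would put one sorting task ahead of a battery covering inhibition, switching and planning, which is a scientific trade-off and not a correction.

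Finally, preferring baseline adjustment to raw change is general advice, and most of the precision gain would exist without the entry rule. That is true, but the gain is available here from data already scheduled. The reply also leaves the wording of the hypothesis, the absence of baseline adjustment, and the undefined score and visits unanswered.

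**Conclusion.** The point holds as a minor one. One D-KEFS administration serves both entry and, by inference from Table 2, the start of the change score, and the plan enters that change unadjusted. The resulting shift is shared by the arms and is small on any fixed test or the five-test mean. It becomes material only if gains are read within CREST on the tests each patient failed. What the plan loses is mainly precision in the treatment-to-mediator step, together with protection against a within-arm reading of a hypothesis worded that way.

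These sizes rest on the assumed SD, reliability and correlations, and on the 73% calibration. The absence of bias in the arm contrast rests on none of them; it follows from randomising after selection. The primary SI-R analysis is unaffected.

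**What to change.** In Hypothesis 2.1:
- Estimate the treatment-to-executive-functioning step as the CREST-minus-ET difference in post-baseline D-KEFS, adjusted for the baseline D-KEFS score, in place of raw change. Name the D-KEFS score and the post-baseline visit or visits used.
- State that a rise in D-KEFS within CREST, especially on tests failed at entry, will not be taken as evidence that the target was engaged.
- Say that the adjustment is for the treatment-to-mediator step, and that it does not by itself validate the mediator-to-outcome step.

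The cost is SAP wording only. Table 2 already schedules every score needed, and neither the sample size nor the primary analysis changes.
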